5.4 Prior and Concomitant Therapy

Any medication or vaccine (including over-the-counter or prescription medicines, vitamins, and/or herbal supplements) that the subject is receiving at the time of enrollment or receives during the study must be recorded on the appropriate electronic case report form (eCRF) from 30 days prior to Baseline

through the 70-day Post-treatment Follow-up Visit. Also, medications taken for PMR since the date of diagnosis and any glucocorticoids (based on subject's recollection and available medical records) should be entered into the appropriate eCRF inclusive of the dates of first and last dose, dosage, route of administration and reason for discontinuation, if known.

Information regarding potential drug interactions with ABBV-154 can be located in the ABBV-154 Investigator's Brochure.¹⁴

Subjects should receive oral calcium and 25-hydroxy vitamin D and/or other therapy for prevention of glucocorticoid-induced osteoporosis in accordance with local standard-of-care practice, unless contraindicated, at the discretion of the investigator. Study participants with documented osteoporosis should be treated with approved drugs for osteoporosis according to local standard-of-care practice or clinical guidelines (e.g., National Osteoporosis Foundation or Japanese Society for Bone and Mineral Research).

See Section 5.8 for concomitant glucocorticoid treatment and rescue treatment for PMR flare.

Vaccines

If the subject and investigator choose to receive/administer live vaccines, these vaccinations must be completed (per local label) at least 28 days (or longer if required locally) before first dose of study drug. Live vaccinations are prohibited during study participation, including at least 70 days after the last dose of study drug. Examples of live vaccines include, but are not limited to, the following:

- Monovalent live influenza A (H1N1) (intranasal);
- Seasonal trivalent live influenza (intranasal);
- Zostavax (herpes zoster, live attenuated);
- Rotavirus;
- Varicella (chicken pox);
- Measles-mumps-rubella or measles-mumps-rubella-varicella;
- Oral polio vaccine;
- Smallpox;
- Yellow fever;
- Bacille Calmette-Guérin (BCG);
- Typhoid (oral).

Administration of inactivated (non-live) vaccines is permitted prior to or during the study according to local practice guidelines. Examples of common vaccines that are inactivated, toxoid or biosynthetic include, but are not limited to, injectable influenza vaccine, pneumococcal, Shingrix (zoster vaccine, recombinant, adjuvanted), and pertussis (Tdap) vaccines.

SARS CoV-2 Vaccination

Given the ongoing COVID-19 pandemic, selected non-live vaccines (e.g., messenger RNA [mRNA], non-replicating viral vector, protein subunit, etc.) to prevent SARS-CoV-2 infection may be administered during screening or the treatment period, as long as components of the vaccine are not contraindicated.

The decision to receive a locally available vaccine should be based on local guidance and an individual discussion between the treating physician and the subject.

The potential impact of ABBV-154 on SARS-CoV-2 vaccination is unknown. Therefore, study drug should be administered as follows:

- The first dose of blinded study drug (ABBV-154/placebo), when possible, is preferred to be given at least ± 7 days from the SARS-CoV-2 vaccine administration.

Note: The above guidance applies to all SARS-CoV-2 vaccine doses given as part of the complete treatment course.

These recommendations may be subject to change based on the evolving knowledge around the use of SARS-CoV-2 vaccines in patients with PMR and as more data are collected in real-world scenarios and clinical trials.

Any SARS-CoV-2 vaccine information must be documented on the COVID-19 vaccine eCRF. Refer to the Operations Manual ([Appendix H](#)) for instructions on reporting any AEs associated with the COVID-19 vaccine.

Inhaled, Intraarticular, and Systemic Glucocorticoids

Inhaled glucocorticoids are allowed for stable medical conditions but must be at stable dose ≥ 4 weeks prior to the Baseline Visit and should remain stable throughout the study. Short-term use (≤ 14 days) of an inhaled glucocorticoid at an increased dose/frequency such as for treatment of an AE is allowed after Week 24 and should not exceed 2 episodes of short-term use through Week 52.

Short-term use (≤ 7 days) of systemic glucocorticoids (including oral, intravenous, intramuscular, intra-articular, intrabursal, tendon sheath, trigger point/tender point, or epidural administration) for non-PMR reasons such as treatment of an AE is allowed only after Week 24, provided the total cumulative dose from Week 24 through Week 52 does not exceed 100 mg prednisone equivalent.

Systemic glucocorticoid use for the treatment of PMR, including rescue therapy, is discussed in [Section 5.8](#).

Nonsteroidal Anti-inflammatory Drugs (NSAIDs) and Analgesics

NSAIDs and analgesics including tramadol, combination of acetaminophen with codeine, or combination of acetaminophen with hydrocodone should continue to be used for the same reason and same dose each time. After Week 24, NSAID and analgesic dosing may be changed. Medication taken on an as-needed basis should not be taken within 24 hours prior to any study visit to avoid bias in outcome measurements.

5.5 Withdrawal of Subjects and Discontinuation of Study

AbbVie may terminate this study prematurely at any time, either in its entirety or partially (discontinue one or more treatment groups), or at any site. The study may be discontinued or terminated in case of an unacceptable risk, any relevant toxicity, or a negative change in the risk/benefit assessment. This might include the occurrence of AEs with a character, severity or frequency that is new in comparison to the existing risk profile. In addition, data derived from other clinical trials or toxicological studies which negatively influence the benefit-risk assessment might cause discontinuation or termination of the study. The investigator may also stop the study at his/her site if he/she has safety concerns. If AbbVie terminates the study for safety reasons, AbbVie will promptly notify the investigator. Advance notice is not required by either party if the study is stopped due to safety concerns.

A subject may voluntarily withdraw from the study at any time for any reason. An investigator may discontinue a subject's participation at any time for any reason. The AbbVie Therapeutic Area Medical Director (TA MD) may mandate individual subject discontinuation from study drug in case of a safety concern.

Subjects must have study drug discontinued immediately if any of the following occur:

- Abnormal laboratory result or AE that meets the criteria for discontinuation of study drug as stated in Section 6.2, or rule out safe continuation of the study drug, as determined by the investigator or the AbbVie TA MD.
- Serious infections (e.g., sepsis) that cannot be adequately controlled within 2 weeks by anti-infective treatment or would put the subject at risk with continuation of study drug.
- Subject is noncompliant with TB prophylaxis (if applicable) or develops active TB at any time during the study.
- Malignancy, except for localized NMSC or carcinoma in-situ of the cervix.
- The subject develops anaphylactic reactions or anaphylactic shock.
- The investigator believes it is in the best interest of the subject.
- The subject requests withdrawal from study drug or the study.
- Eligibility criteria violation was noted after the subject started study drug and continuation of the study drug would place the subject at risk.
- Introduction of prohibited medications or dosages and continuation of the study drug would place the subject at risk.
- The subject becomes pregnant while on study drug.
- Subject is significantly noncompliant with study procedures, which would put the subject at risk for continued participation in the trial as determined by the Investigator or AbbVie TA MD.
- Subject is prematurely unblinded to study drug assignment by the investigator or AbbVie TA MD.
- Subject requires the addition of prohibited immunomodulatory medication for treatment of PMR.

- Diagnosis of GCA.

When the blinded study drug (ABBV-154/placebo) is discontinued, the Sponsor-supplied prednisone/prednisolone must also be discontinued. Prednisone/prednisolone may then be prescribed by the investigator, with dosing based on the investigator's judgement and in accordance with local standard of care. Medications prescribed by the investigator should be documented on the concomitant medication eCRF.

Additional requirements related to abnormal laboratory values and selected specific AEs (safety topics of interest) are located in Section 6.2.

COVID-19 Pandemic-Related Acceptable Protocol Modification

During the COVID-19 pandemic, it may be necessary to employ mitigation strategies to enable the investigator to ensure subject safety and continuity of care. Acceptable mitigation strategies are identified and included in the Operations Manual in [Appendix H](#).

The investigator should contact the sponsor medical contact before discontinuing a subject from the study for a reason other than "planned per protocol," to ensure all acceptable mitigation steps have been explored. Refer to the Operations Manual in [Appendix H](#) for details on how to handle study activities/procedures.

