5.3 Prohibited Medications and Therapy

Subjects must be able to safely discontinue any prohibited medications as specified in Section 5.1 and Section 5.4. Subjects must be consented for the study prior to discontinuing any prohibited medications for the purpose of meeting study eligibility.

Intra-articular, intra-bursal, tendon sheath, trigger point or tender point, or epidural administration of glucocorticoids are not permitted prior to Week 24.

The following medications are prohibited through the end of study drug administration:

1. Systemic glucocorticoids (including but not limited to oral, intravenous, intramuscular), except as permitted as outlined in Section 5.1, Section 5.4, and Section 5.8.
2. Super-high potency and high potency topical glucocorticoids (see Appendix E).
3. Corticotropin gel injection (i.e., Acthar®)
4. Biologic Therapies: Subjects must have discontinued biologic therapies prior to the first dose of study drug as specified in the washout procedures (Eligibility Criterion 27 in Section 5.1). For all other biologic therapies, the required washout period is at least five times the mean terminal elimination half-life of the medication prior to Baseline. No minimum washout prior to Baseline is required for a biologic therapy if an undetectable drug level measured by a commercially available assay is documented. Therapies including but not limited to the following biologic therapies are prohibited medications through the end of study drug administration:

- Abatacept
 - Adalimumab
 - Anakinra
 - Belimumab
 - Certolizumab
 - Dupilumab
 - Etanercept
 - Golimumab
 - Infliximab
 - Ixekizumab
 - Natalizumab
 - Rituximab
 - Risankizumab
 - Sarilumab
 - Secukinumab
 - Tocilizumab
 - Ustekinumab
 - Vedolizumab
5. Conventional and targeted synthetic disease-modifying antirheumatic drugs (DMARDs):
Subjects must have discontinued conventional and targeted synthetic DMARD therapies prior to Baseline as specified in the washout procedures (see Eligibility Criteria in Section 5.1), except for hydroxychloroquine. For all other conventional or targeted synthetic DMARDs, the required washout period is at least five times the mean terminal elimination half-life of the medication prior to Baseline.
 6. Investigational drugs.
 7. Live vaccination (see Section 5.4 for examples of live vaccines).
 8. Any opiate analgesics with the exception of tramadol, combination of acetaminophen with codeine, or combination of acetaminophen with hydrocodone.

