5.6 Follow-Up After Subject Discontinuation of Study Drug or from Study

Discontinuation of Study Drug and Continuation of Study Participation

To minimize missing data for efficacy and safety assessments, subjects who prematurely discontinue study drug treatment should be encouraged to continue to be followed for all regularly scheduled visits (except for visits that are intended only for study drug administration [Weeks 6, 10, 14, 18, 22, 26, 30, 34, 38, 42, 46, and 50]), unless the subject has decided to discontinue the study participation entirely (withdrawal of informed consent). At the visits after study drug discontinuation, subjects should adhere to all study procedures except for dispensing of study drug and accountability, dosing diaries, and PK (conjugated ADC, total antibody, free A-1677770 assays) and immunogenicity (ADA assays) sample collection. Subjects should be advised on the continued scientific importance of their data even if they discontinue treatment with study drug early. Following discontinuation of study drug, the subject should be treated in accordance with the investigator's best clinical judgment irrespective of whether the subject decides to continue participation in the study.

If a subject prematurely discontinues study drug, the procedures outlined for the Premature Discontinuation Visit should be completed as soon as possible, preferably within 2 weeks, and preferably prior to initiation of another therapy.

In addition, a 30-day Follow-up Phone Call and 70-Day Follow-up Visit after the last dose of study drug is required to ensure all treatment-emergent AEs/SAE have been resolved. All attempts must be made to determine the date of the last study drug dose and the primary reason for discontinuation of study drug or study participation. This information will be recorded on the appropriate eCRF page. This Follow-up

Phone Call is not applicable for subjects who discontinued study drug prematurely and continued study participation with completion of at least 1 study visit that was at least 30 days after the last dose of study drug. This visit is not applicable for subjects who discontinued study drug prematurely and continued study participation with completion of at least 1 study visit that was at least 70 days after the last dose of study drug.

Premature Discontinuation of Study (Withdrawal of Informed Consent)

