If a subject has a suspected PMR flare at any time during the study, the flare should be confirmed as soon as possible, prior to initiating glucocorticoid rescue treatment. Flare may be confirmed at either a scheduled visit or unscheduled visit. Assessments performed at a visit for suspected flare are listed in Section 5.7 and in the Operations Manual (Appendix H). Additional assessments may be added per the investigator's medical judgement. PMR must be confirmed as the cause of flare by eliminating other causes of the subject's symptoms/signs such as infection or other underlying disease. Once flare is confirmed, glucocorticoid rescue should be administered with the dose and subsequent tapering at the discretion of the investigator, taking into consideration local standard of care, the subject's preflare and/or baseline dose, and not exceeding 15 mg/day. The investigator must record his/her recommendation to increase the prednisone/prednisolone dose due to PMR flare in the eCRF, regardless of whether or not the subject agrees to increase his/her dose. The specific dose of glucocorticoid rescue therapy taken by the subject should be documented in the eCRF.

While receiving open-label rescue treatment with prednisone/prednisolone, the subject should continue in the study and receive blinded study drug (ABBV-154/placebo) unless the subject meets the study drug discontinuation criteria (see Section 5.5).

If a subject remains on prednisone/prednisolone up to the Week 52 visit, the subject will take the last dose of Sponsor-supplied prednisone/prednisolone on the day prior to the Week 52 or on the day of the Week 52 visit and may restart individually-sourced prednisone equivalent on or after the day of the Week 52 visit, under the medical guidance of the investigator.

Addition of immunomodulators other than glucocorticoid rescue, as outlined above, are not permitted for rescue. If the investigator determines it is in the best interest of the subject to start an immunomodulator, the subject must discontinue study drug treatment (ABBV-154/placebo and sponsor-supplied prednisone/prednisolone). Any subsequent medications prescribed by the investigator should be documented on the concomitant medication eCRF.

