7.3 Handling Potential Intercurrent Events for the Primary and Secondary Endpoints

Primary endpoint:

- Subjects will be censored at the time of immunomodulator initiation or violation of protocol-allowed systemic glucocorticoid use.

Categorical secondary endpoints:

- Subjects will be considered as not achieving the response after the initiation of rescue medication, immunomodulator or violation of protocol-allowed systemic glucocorticoid use.

Continuous endpoint:

- No intercurrent event will be considered in the analysis of glucocorticoid dose.

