### **8.0 Handling of Potential Intercurrent Events for the Primary and Secondary Endpoints**

The primary efficacy endpoint (defined in Section 3.1) will be analyzed based on the ITT population and subjects will be censored at the time of the last available assessment, initiation of immunomodulator, or violation of protocol-allowed systemic glucocorticoid use.

The categorical secondary efficacy endpoint (defined in Section 3.2) will be analyzed based on the ITT population and the following methods will be used to address the potential intercurrent events:

- Subjects will be considered as not achieving the response after the initiation of rescue medication, immunomodulator or violation of protocol-allowed systemic glucocorticoid use.

The continuous secondary efficacy endpoints (defined in Section 3.2) will be analyzed based on the ITT population and the following methods will be used to address the potential intercurrent events:

- No intercurrent event will be considered in the analysis of glucocorticoid dose.

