**9.4 Secondary Efficacy Endpoints and Analyses**

**9.4.1 Secondary Efficacy Endpoints**

The categorical secondary endpoint is

- Achievement of flare-free state up to Week 24

The continuous secondary endpoints are

- Cumulative glucocorticoid dose by 24 weeks

- Change from Baseline in glucocorticoid dose at Week 24

For the analysis of glucocorticoid dose, all systemic glucocorticoid use will be included regardless of the indication.

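### Systemic glucocorticoid above the taper, taken after study drug stops and without a declared flare, is on the plain reading not an intercurrent event, so such subjects stay event-free and count as Week 24 responders

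*Protocol*

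**What the plan says.** **After study drug stops.** Protocol 5.5 requires sponsor-supplied prednisone to stop as well, then adds: "Prednisone/prednisolone may then be prescribed by the investigator, with dosing based on the investigator's judgement", in line with local standard of care. It states no ceiling. For rescue in subjects on study drug, Protocol 5.8 does set one: "not exceeding 15 mg/day". Protocol 5.3 introduces its list, which includes systemic glucocorticoids, with: "The following medications are prohibited through the end of study drug administration". The change log (Protocol Appendix G) explains that subjects may receive these medicines after stopping study drug, and that rescue rules no longer apply to those who stop and stay in the study.

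**Follow-up continues.** Under Protocol 5.6, "subjects who prematurely discontinue study drug treatment should be encouraged to continue to be followed for all regularly scheduled visits". Flare assessment is not among the procedures dropped.

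**Intercurrent events.** For time to flare, Protocol 7.3 says: "Subjects will be censored at the time of immunomodulator initiation or violation of protocol-allowed systemic glucocorticoid use". For flare-free state up to Week 24, SAP 8.0 says: "Subjects will be considered as not achieving the response after the initiation of rescue medication, immunomodulator or violation of protocol-allowed systemic glucocorticoid use". SAP Tables 1 and 2 repeat these lists. Study-drug discontinuation is on neither, and no document defines what counts as a violation.

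**Text pointing the other way.** Protocol 4.1 keeps subjects off prednisone from the end of the taper to Week 52 unless flare is confirmed. Protocol 5.4 allows short systemic courses for non-PMR reasons only after Week 24. Neither is expressly confined to subjects on study drug.

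**The concern.** The trial asks whether disease stays controlled while glucocorticoid is withdrawn on an identical taper in every arm. Systemic glucocorticoid above that taper can suppress the symptoms that define a flare.

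For a subject on study drug, a systemic course for a non-PMR reason before Week 24 falls outside what Protocol 5.4 allows. It therefore leads to censoring in the primary analysis and non-response in the binary secondary. The same course the day after study drug stops is expressly permitted by Protocol 5.5, and so, on the plain reading, triggers neither.

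The exposure is foreseeable. Protocol 6.2 anticipates glucocorticoid for adrenal insufficiency and in situations of stress, including the months after study drug is withdrawn.

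At stake are the Week 24 flare-free difference and, to a lesser degree, the hazard ratio. SAP 9.6 takes response rates from the primary analysis approach into the dose-response modelling, so the classification carries through to it. SAP 9.3.3 and 9.4.3 plan no sensitivity analysis that would show the effect.

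**Working it through.** **1. The plan's own figure.** Inputs (Protocol 7.10, SAP 2.4): 70% and 30% flare-free at Week 36 on the highest dose and placebo, 37 flares, 2-sided alpha 0.1.

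- Hazard ratio = ln(0.70)/ln(0.30) = 0.296, as stated.
- Power (Schoenfeld): √(37/4) × |ln 0.296| − 1.645 = 2.06, which gives 98.0%. Freedman's form gives 95.1%. Both agree with the stated figure of more than 90%.

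**2. Flare-free state at Week 24.** Assumptions, none of them in the documents: constant hazards; a share d of each arm stops study drug at Week 8; no leaver flares afterwards; all stay in follow-up.

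- S(24) = 0.3^(24/36) = 44.8% on placebo and 0.7^(24/36) = 78.8% on high dose, a difference of 34.0 points with no leavers.
- S(8) = 0.3^(8/36) = 76.5% and 0.7^(8/36) = 92.4%.
- As written: (1 − d) × S(24) + d × S(8).
- Every leaver a non-responder: (1 − d) × S(24).

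| Leaving, high dose / placebo | As written: high, placebo, difference | Leavers non-responders: high, placebo, difference |
|---|---|---|
| 20% / 5% | 81.5, 46.4, **35.1** | 63.1, 42.6, **20.5** |
| 15% / 15% | 80.9, 49.6, **31.3** | 67.0, 38.1, **28.9** |
| 5% / 20% | 79.5, 51.2, **28.4** | 74.9, 35.9, **39.0** |

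Differences are in percentage points, taken before rounding. The gap between the two rules is d × S(8) on high dose minus d × S(8) on placebo. In the first row that is 18.5 − 3.8 = 14.7 points. Its sign follows the imbalance in d.

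**3. Time to flare.** Simulation of 20,000 trials: 40 per arm, exponential flare times, unstratified log-rank at 2-sided 0.1, follow-up to Week 36. An assumed share stops at a uniform time in Weeks 0 to 24 and, if not yet flared, is fully masked. The two right-hand columns treat the stop as a censoring time or as an event.

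| Effect; share stopping, placebo / high dose | As written | Censored | Event |
|---|---|---|---|
| Design effect, 10% / 10%: power | 97.4% | 97.9% | 95.6% |
| Design effect, 20% / 20%: power | 96.1% | 97.1% | 91.0% |
| Design effect, 30% / 30%: power | 94.4% | 96.1% | 84.8% |
| No effect, 10% / 20%: significant in favour of drug | 9.1% | 5.1% | 2.2% |
| No effect, 10% / 30%: significant in favour of drug | 15.0% | 5.0% | 0.8% |
| No effect, 20% / 10%: significant in favour of drug | 2.5% | 5.0% | 10.7% |

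With nobody stopping, power is 98.4%. The nominal rate in the no-effect rows is 5%. Censoring holds it here because the simulated stops are unrelated to flare risk, which a real trial does not guarantee.

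**The case against.** The strongest reply is that the misclassification is inferred. Since the violation term is undefined and Protocol 4.1 and 5.4 are not limited to subjects on study drug, a programmer could code the same prednisone as a violation. The relevant Operations Manual section is not in the public documents. This stands, and it is why the passages have to be reconciled: two programmers could score one subject differently.

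Second, much of the exposure is already handled:

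- PMR symptoms with a required dose increase are still a flare after discontinuation.
- Starting an immunomodulator is already an intercurrent event.
- Subjects who leave the study are generally non-responders under NRI-MI (SAP 9.2.2).
- In the two glucocorticoid-dose secondaries, "all systemic glucocorticoid use will be included regardless of the indication" (SAP 9.4.1).

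This also stands. What remains is glucocorticoid above the taper, without a declared flare, in subjects who stay in follow-up.

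Third, the figures overstate. They score every leaver as a non-responder, whereas the rule below reaches only those above the taper, and they assume complete masking. The plan as written also lies closer to the no-leaver 34.0 points in two of the three rows. Part of the gap is thus a change of estimand rather than bias. That is fair, and the figures should be read as upper-end illustrations.

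Fourth, steroid given for adrenal insufficiency or stress says little about PMR control, so calling it non-response is debatable. This carries less weight: the plan already does so for a subject on study drug before Week 24.

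**Conclusion.** The gap holds on the plain reading, for a defined group: subjects who stop study drug, stay in follow-up and take systemic glucocorticoid above the scheduled taper without a declared flare. In the primary analysis they stay in the risk set without an event and are later censored. In the binary secondary, if assessed, they are responders. It should be closed before unblinding.

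A reader might infer more than the documents support:

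- **That any dose is allowed.** Protocol 5.5 ties dosing to local standard of care, although it states no cap.
- **That the result is tilted towards the drug.** No discontinuation rates are given. More masking on the drug favours it, and more on placebo works against it.
- **That the power statement fails.** Equal masking of 10% to 30% costs about 1 to 4 points, leaving 94.4% or more.
- **That the secondaries as a whole are exposed.** Only one of the three is.

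The Week 24 difference moves from 35.1 to 20.5, 31.3 to 28.9, or 28.4 to 39.0 points. Those sizes rest on the assumed leaving rates, full masking from Week 8 and every leaver being scored a non-responder.

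**What to change.** 1. In SAP 8.0 and Table 2, define the glucocorticoid intercurrent event as systemic glucocorticoid above the scheduled taper dose, whether before or after study-drug discontinuation. Count it as non-response for flare-free state up to Week 24, in keeping with the composite rule already there. Say how the short non-PMR courses that Protocol 5.4 allows after Week 24 fit this definition at later visits.
2. In SAP 8.0 and Table 1, have the sponsor state the main strategy for this use in time to flare. Table 1 is labelled composite but censors, so the intention is not clear at present.
3. In SAP 9.3.3, replace the not-applicable entry with two supplementary analyses: (a) this use counted as an event, and (b) censoring at it. The simulation shows why both are wanted. Event counting penalises the arm with more stops, and censoring relies on stops being unrelated to flare risk.
4. Reconcile Protocol 4.1 and 5.4 with 5.3 and 5.5 before unblinding. This point does not say which reading is right.

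The cost is SAP wording and two extra analyses. Dosing diaries stop after discontinuation (Protocol 5.6), but Protocol 5.5 already puts investigator-prescribed medication on the concomitant medication eCRF. The downside is lower flare-free rates in arms with more discontinuation, possibly not slight: 81.5% to 63.1% on high dose in the first illustration. Some steroid given for non-PMR reasons will also count as non-response.
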